10.1.15 Visit 31 (Week 64, End of Study Visit)

- Record all concomitant medication use; inquire about AEs/SAEs and background asthma therapy tolerability
- Measure vital signs (blood pressure, heart rate, respiratory rate, body temperature, weight and height)
- Perform physical examination
- Obtain urine for urinalysis (dipstick)
- Assess menstruation status and perform urine dipstick pregnancy test for female patients of childbearing potential (who have commenced menstruating)
- Administer ACQ-7
- Administer all additional PROs:
PAQLQ(S)-IA, PRQLQ-IA, EQ-5D-Y for children, PACQLQ

- Administer HCRU
- Measure exhaled nitric oxide
 - Exhaled nitric oxide assessment is conducted prior to spirometry and following a fast of ≥ 1 hour.
- Perform spirometry
 - Spirometry will be performed at approximately the same time of last visit after a wash out period of bronchodilators according to their action duration, for example, withholding the last dose of salbutamol/albuterol or levosalbutamol/levalbuterol for at least 6 hours, withholding the last dose of LABA for at least 12 hours, and withholding the last dose of LAMA for at least 24 hours. This will be verified before performing the PEF measurements.
 - Post-bronchodilator FEV1 should be determined.
- Perform 12-lead ECG
- Perform blood sampling for the following tests:
 - Clinical laboratories,
 - Systemic drug concentration,
 - ADAs
- Download electronic diary/PEF meter and take back the device
- Call IVRS/IWRS to register the EOS date

10.2 DEFINITION OF SOURCE DATA

Source data is all information in original records and certified copies of original records of clinical findings, observations, or other activities in a clinical trial necessary for the reconstruction and evaluation of the trial. Source data are contained in source documents. Source documents are original documents, data and records such as hospital records, clinic and office charts, laboratory notes, memoranda, pharmacy dispensing records, recorded data from automated instruments, etc.

All the data collected in the e-CRF should be transcribed directly from source documents. Data downloaded from the study-associated central laboratories, spirometry, nitric oxide measurement, ECG, and patient electronic diary/PEF meter will be considered source data.

10.3 HANDLING OF PATIENT TEMPORARY OR PERMANENT TREATMENT DISCONTINUATION AND OF PATIENT STUDY DISCONTINUATION

The IMP should be continued whenever possible. In case the IMP is stopped, it should be determined whether the stop can be made temporarily; permanent IMP discontinuation should be a last resort. Any IMP discontinuation should be fully documented in the e-CRF. In any case, all efforts should be made to maintain the patient for the 12 weeks follow up.

10.3.1 Temporary Treatment Discontinuation With Investigational Medicinal Product(s)

Temporary treatment discontinuation may be considered by the Investigator because of AEs. Reinitiation of treatment with the IMP will be done under close and appropriate clinical and/or laboratory monitoring once the Investigator will have considered according to his/her best medical judgment that the responsibility of the IMP(s) in the occurrence of the concerned event was unlikely and if the selection criteria for the study are still met (refer to [Section 7.1](#) and [Section 7.2](#)) AE is sufficiently resolved and unlikely to recur after resuming therapy with IMP.

In addition, the following conditions(s) will be cause for temporary treatment discontinuation:

- Infections or infestations that do not respond to medical treatment
- Any laboratory abnormality that meets temporary treatment discontinuation criteria as per [Appendix K](#) on Guidelines for management of specific laboratory abnormalities

10.3.2 Permanent Treatment Discontinuation With Investigational Medicinal Product(s)

Permanent treatment discontinuation is any treatment discontinuation associated with the definitive decision from the Investigator or the patient not to re-expose the patient to the IMP at any time.

10.3.3 List of Criteria for Permanent Treatment Discontinuation

The patients may withdraw from treatment with the IMP if they decide to do so, at any time and irrespective of the reason, or this may be the Investigator's decision. All efforts should be made to document the reasons for treatment discontinuation and this should be documented in the CRF or e-CRF.

Patients must be withdrawn from the study (ie, from any further investigational product or study procedure) for the following reasons:

- At their own request or at the request of their legally authorized representative (Legally authorized representative means an individual or judicial or other body authorized under applicable law to consent on behalf of a prospective patient to the patient's participation in the procedure(s) involved in the research).
- If, in the Investigator's opinion, continuation in the study would be detrimental to the patient's well-being
- At the specific request of the Sponsor
 - Including some specific circumstances like the Yellow Fever outbreak in Brazil, where patients from affected areas who are not previously vaccinated with yellow-fever vaccine, are to be permanently discontinued from study drug ([Section 8.8.1](#)).
- In the event of a protocol deviation, at the discretion of the Investigator or the Sponsor
- Any code breaking requested by the Investigator will lead to permanent treatment discontinuation.
- Pregnancy

- Anaphylactic reactions or systemic allergic reactions that are related to IMP and require treatment.
- Diagnosis of a malignancy during study.
- Any opportunistic infection, such as TB or other infections whose nature or course may suggest an immunocompromised status (See [Appendix M](#)).
- Serum ALT >3 ULN and Total Bilirubin >2 ULN (See [Appendix K](#)).
- Serum ALT >5 ULN if baseline ALT <2 ULN or ALT >8 ULN if baseline ALT >2 ULN ([Appendix K](#)).

Any abnormal laboratory value or ECG parameter will be immediately rechecked for confirmation before making a decision of permanent discontinuation of the IMP for the concerned patient.

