8.3.2 Randomization code breaking during the study

In case of an AE, the code should only be broken in circumstances when knowledge of the IMP is required for treating the patient.

Code breaking can be performed at any time by using the proper module of the interactive voice response system (IVRS)/interactive web response system (IWRS) and/or by calling any other phone number provided by the Sponsor for that purpose. If the blind is broken, the Investigator should document the date, time of day and reason for code breaking.

Patient withdrawal will only occur when the code break call is made at the site level, not the study level. This means that if the Emergency Unblinding transaction is performed by the Investigator (ie, at the site level), then the subject will be withdrawn from treatment. However, if the Emergency Unblinding transaction is performed by the Global Safety Officer (GSO) (ie, at the study level, as the GSO is not site based), then the subject will not be withdrawn from treatment.

At the facilities where the systemic drug concentration measurements, ADAs and selected biomarkers are determined, the samples will be analyzed prior to data base lock leading to unblinding of responsible bioanalysts. Bioanalysts are excluded from the clinical trial team.

Patient(s)/parent(s)/caregiver(s)/legal guardian(s), Investigators, and site personnel will not have access to assay results for immunoglobulins (immunoglobulin G (IgG), IgG subclasses, Immunoglobulin A (IgA), IgM and IgE) after randomization and first administration of study medication, because these values have the potential for unblinding. Furthermore, neither patient(s)/parent(s)/caregiver(s)/legal guardian(s), Investigators nor site personnel will have access to total IgE, antigen-specific IgE, antigen-specific IgG4, Thymus and Activation-Regulated Chemokine (TARC) while the study is ongoing, as the related data are not essential for patient care and have the potential for unblinding.

The DMC will receive blinded by treatment group or unblinded (if necessary) confidential reports from an independent statistician for review, which have to be handled strictly confidentially. None of these reports can be delivered to unauthorized persons.

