10.3.4 Handling of Patients After Permanent Treatment Discontinuation

Patients will be followed-up according to the study procedures as specified in this protocol up to the scheduled date of study completion, or up to recovery or stabilization of any AE to be followed-up as specified in this protocol, whichever comes last. Study Investigators should continue background therapy after treatment discontinuation, as guided by their medical judgment.

For patients in Brazil, see [Appendix N](#).

Patients who permanently discontinue the study medication will be asked and encouraged to return to the clinic for study visits and participate in assessments according to the visit schedule until the EOS with a ± 5 day window or up to recovery or stabilization of any AEs. At the time of permanent treatment discontinuation, patients will perform ETD visit with all the assessments defined for the EOT Visit 28. Patients who permanently discontinue early from treatment will not be eligible for the 1-year long-term extension study.

For patients who permanently discontinue the study, under exceptional circumstances where there is no possibility for a patient and parent(s)/caregiver(s)/legal guardian(s) to come to the site for the scheduled follow-up visit, a phone contact may be made after Sponsor's approval is given. During that phone contact, at least information about AEs, concomitant medication and asthma exacerbation events must be collected, and the schedule for these calls should still reflect the visit schedule.

Patients who discontinue early from treatment may be asked to return to the clinic to have additional ADA samples collected for analysis based on the overall assessment of antibody titers and clinical presentation at the time of discontinuation.

All cases of permanent treatment discontinuation should be entered by the Investigator in the e-CRF when considered as confirmed.

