10.3.5 Procedure and Consequence for Patient Withdrawal From Study

The patients may be withdrawn from the study at any time during the course of study if their parent(s)/caregiver(s)/legal guardian(s) decide to do so, and irrespective of the reason.

Withdrawal of consent for follow-up should be accompanied by documentation of the reason for withdrawal. Withdrawal of consent for treatment should be distinguished from withdrawal of consent for follow-up visits and from withdrawal of consent for non-patient contact follow-up, eg, medical records checks.

For patients who withdraw, the patient and their parent(s)/caregiver(s)/legal guardian(s) should be explicitly asked about the contribution of possible AEs to their decision to withdraw consent, and any AE information elicited should be documented.

Patient(s)/parent(s)/caregiver(s)/legal guardian(s) may withdraw consent verbally or in writing and, if verbal, then the site needs to document in source records that patient withdrew consent verbally.

If possible, the patients who withdraw consent will be assessed using the procedures normally planned for the EOT visit and have EOS assessments completed at the same visit or at the last planned visit.

For patients who fail to return to the site, the Investigator should make the best effort to re-contact the patient (eg, contacting patient's family or private physician, reviewing available registries or health care databases), and to determine his/her health status, including at least his/her vital status. Attempts to contact such patients must be documented in the patient's records (eg, times and dates of attempted telephone contact, receipt for sending a registered letter).

A subject should only be designated as lost to follow-up, if the site is unable to establish contact with the patient/parent(s)/caregiver(s)/legal guardian(s) after 3 documented attempts via 2 different methods (phone, text, e-mail, certified letter, etc).

The statistical analysis plan (SAP) will specify how these patients lost to follow-up for their primary endpoints will be considered. Patients who have withdrawn from the study cannot be rerandomized (treated) in the study. Their inclusion and treatment numbers must not be reused.

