10.4.1.3 Adverse Event of Special Interest

An AESI is an AE (serious or nonserious) of scientific and medical concern specific to the Sponsor's product or program, for which ongoing monitoring and immediate notification by the Investigator to the Sponsor is required. Such events may require further investigation in order to characterize and understand them. Adverse events of special interest may be added, modified or removed during a study by protocol amendment.

- Anaphylactic reactions or systemic allergic reactions that are related to IMP and require treatment (refer to [Appendix L](#) for the definition of anaphylaxis).
- Severe injection site reactions that last longer than 24 hours.
- An infection that meets at least one of the following criteria:
 - Any serious infection (that meet any of the SAE criteria)
 - Requires parenteral (intravenous, intramuscular, SC) antimicrobial therapy.
 - Requires oral antimicrobial therapy for >2 weeks.
 - Is a parasitic infection.
 - Is an opportunistic infection (see list in [Appendix M](#)).

Note: antimicrobial therapy refers to antibiotic, antiviral, and antifungal agents.

- Significant elevation of ALT ([Appendix K](#))
 - $ALT > 5 \times ULN$ in patients with baseline $ALT \leq 2 \times ULN$; or
 - $ALT > 8 \times ULN$ if baseline $ALT > 2 \times ULN$
- Pregnancy occurring in a female patient entered in the clinical trial or in a female partner of a male patient entered in the clinical trial (It is an unlikely event to happen but for safety concerns, it is imperative to query pregnancy involving a male patient entered in the trial).
 - It will be qualified as an SAE only if it fulfills 1 of the seriousness criteria (see [Section 10.4.1.2](#)).
 - In the event of pregnancy in a female participant, IMP should be discontinued.
 - Follow-up of the pregnancy in a female participant or in a female partner of a male participant is mandatory until the outcome has been determined.
- Symptomatic overdose (serious or non-serious) with IMP/NIMP
 - An overdose (accidental or intentional) with the IMP/NIMP is an event suspected by the Investigator or spontaneously notified by the patient (not based on systematic pills count) and defined as at least twice the intended dose during an interval of less than 11 days. The circumstances (ie, accidental or intentional) should be clearly specified in the verbatim and symptoms, if any, entered on separate AE forms.

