10.4.3 General Guidelines for Reporting Adverse Events

- All AEs, regardless of seriousness or relationship to IMP/NIMP, spanning from the signature of the informed consent form until the end of the study as defined by the protocol for that patient, are to be recorded on the corresponding page(s) or screen(s) of the e-CRF.
- When a safety event is categorized as a primary outcome, the event will be reported as an AE but will be waived from reporting to regulatory authorities provided an agreement has been reached with them.
- Whenever possible, diagnosis or single syndrome should be reported instead of symptoms. The Investigator should specify the date of onset, intensity, action taken with respect to IMP, corrective treatment/therapy given, additional investigations performed, outcome, and his/her opinion as to whether there is a reasonable possibility that the AE was caused by the IMP or by the study procedure(s). In studies that require the use of combined/multiple IMPs/NIMPs, the GSO with input from other appropriate study team members must determine if the causal relationship will either be assessed for the combined product as a regimen or as distinct entities. The GSO must communicate this decision to the study team for inclusion in the protocol and AE CRF.
- The Investigator should take appropriate measures to follow all AEs until clinical recovery is complete and laboratory results have returned to normal, or until progression has been stabilized, or until death, in order to ensure the safety of the patients. This may imply that observations will continue beyond the last planned visit per protocol, and that additional investigations may be requested by the monitoring team up to as noticed by the Sponsor. Patients who experience an ongoing SAE or an AESI, at the prespecified study end-date, should be followed until resolution, stabilization, or death and related data will be collected. The duration of poststudy follow-up and reporting of AEs will be specified (eg, until recovery).
- When treatment is prematurely discontinued, the patient's observations will continue until the end of the study as defined by the protocol for that patient.
- Laboratory, vital signs or ECG abnormalities are to be recorded as AEs only if:
 - Symptomatic and/or

- Requiring either corrective treatment or consultation, and/or
- Leading to IMP discontinuation or modification of dosing, and/or
- Fulfilling a seriousness criterion, and/or
- Defined as an AESI

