10.6 SAFETY INSTRUCTIONS

10.6.1 Hypersensitivity

Allergic reaction is a potential risk associated with the administration of most therapeutic monoclonal antibodies.

Allergic reactions may be defined as allergic reaction-mediated signs and symptoms experienced by patients during or shortly after the pharmacologic or biologic agent given. These reactions may present in a variety of ways, including dizziness, headache, anxiety, dyspnea, hypotension, tachycardia, pruritus, rash, urticaria/angioedema, flushing, nausea, or vomiting. Anaphylaxis may represent the most severe form of infusion reaction, but these events may also occur via non-IgE mediated mechanisms (eg, anaphylactoid reactions), or may occur via other immune-mediated mechanisms (eg, cytokine-mediated). Refer to [Appendix L](#) “Definition of Anaphylaxis”, which describes the clinical criteria for the diagnosis of anaphylaxis.

Patients must be monitored for at least 30 minutes after each study-site administered investigational product administration for any signs or symptoms of a hypersensitivity reaction. Trained personnel and medications should be available to treat anaphylaxis or any severe allergic reaction if it occurs. Furthermore, the patients will be advised, when the IMP is administered at home, to self-monitor for potential signs and symptoms that may suggest a hypersensitive reaction for at least 30 minutes after administration.

Anaphylactic reactions or, systemic allergic reactions that are related to IMP and require treatment must be reported as an AESI (within 24 hours, for further details, see AESI definition in [Section 10.4.1.3](#) and [Appendix L](#)) and study medication should be permanently discontinued. Anti-drug antibodies and PK samples will be collected near the onset and resolution of the AESI for any additional analysis.

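### The lead sentence of Protocol 10.3.3 orders study withdrawal for criteria that other sections treat as stopping IMP only: wrong as written, with a small consequence for the primary analysis

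*Protocol*

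**What the plan says.** The heading of Protocol 10.3.3, its opening paragraph and its closing sentence all concern stopping IMP. The sentence that introduces the list does not: "Patients must be withdrawn from the study (ie, from any further investigational product or study procedure) for the following reasons". Eleven bullets follow. Two of them revert to treatment language: the code-break bullet, and the yellow-fever item placed under Sponsor request.

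The next section, 10.3.4, sets out what happens once IMP has been stopped for good: "Patients will be followed-up according to the study procedures as specified in this protocol up to the scheduled date of study completion". It adds an early-discontinuation visit and return to the visit schedule. The trial summary, the flow chart footnotes and Section 10 repeat this. Section 10.4.3 says that when treatment stops early the patient's "observations will continue until the end of the study as defined by the protocol for that patient". Section 10.3.5 adds: "Withdrawal of consent for treatment should be distinguished from withdrawal of consent for follow-up visits".

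The primary analysis (Protocol 11.4.2.1; SAP 2.4.4.1 and Table 6) is treatment policy. Severe exacerbations after stopping treatment count up to Week 52. A patient who leaves the study is observed only to last contact, and later events are not imputed.

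**The concern.** A Protocol section headed as treatment discontinuation tells the site to end all study procedures. The bracketed explanation in the lead sentence rules out reading it as loose wording for stopping the drug. The next section says the opposite, and a site cannot follow both for the same patient.

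The estimand depends on the difference. A patient who stops IMP and stays in the study contributes off-treatment exacerbations. The same patient withdrawn from the study becomes missing from last contact. If the drug effect wanes after stopping, the uncollected dupilumab events are those closest to the placebo rate, and their loss favours dupilumab. The list also puts consent withdrawal together with medical stopping rules, which 10.3.5 asks sites to keep apart.

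**Working it through.** **Text comparison.** Each bullet of 10.3.3 against what the protocol says elsewhere:

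| Bullet in 10.3.3 | Other text | Consequence stated there |
|---|---|---|
| Own or representative's request | 10.3.5 | Depends on whether consent is withdrawn for treatment or for follow-up |
| Continuation detrimental | none | A proper reason for study withdrawal |
| Sponsor request | Appendix N, yellow fever only | IMP stop, followed to end of study |
| Protocol deviation | none | Discretionary |
| Code break by the Investigator | 8.3.2 | "then the subject will be withdrawn from treatment" |
| Pregnancy | 10.4.1.3 | "In the event of pregnancy in a female participant, IMP should be discontinued" |
| IMP-related allergic reaction | 10.6.1 | "study medication should be permanently discontinued", with later samples near resolution |
| Malignancy | none | none |
| Opportunistic infection | 10.6.3 | Stop study medication permanently |
| Two ALT/bilirubin criteria | Appendix K | Liver tests monitored after IMP stops, so continued contact is presupposed |

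Four bullets and the yellow-fever item have explicit text that stops IMP. The two ALT bullets have indirect support.

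**Plan's own figure.** Linear discontinuation reaching 20% at one year gives average exposure 1 - 0.20/2 = 0.9 year, as Protocol 11.1 states. The planned loss is therefore 0.1 year per patient: 0.1 x 345 = 34.5 patient-years in the Type 2 population, and 0.1 x 255 = 25.5 in the population with eosinophils >=0.3 Giga/L (sizes from SAP 1.1).

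**Inputs for the size.** The current planning rates are redacted. The superseded values shown in Protocol Appendix O and SAP 1.5 serve as a scale only: placebo rate 1.0 per year, dupilumab rate 0.5, dispersion 1.5, allocation 2:1. With 294 patients and 0.9 year they give power 0.9006, against the 90% stated for that design.

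Var(log RR) = (1/(1.0 x 0.9) + 1.5)/n_placebo + (1/(0.5 x 0.9) + 1.5)/n_dupilumab

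- Type 2, 115 and 230: 2.611/115 + 3.722/230 = 0.0389, SE 0.197.
- Eosinophils >=0.3 Giga/L, 85 and 170: 2.611/85 + 3.722/170 = 0.0526, SE 0.229.

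**Shift in the estimate.** Let f be the fraction meeting a criterion at mid-year (assumed 1% to 5%), c the share of them withdrawn from the study, and p the years for which the drug effect persists. The dupilumab rate that the estimand should measure is 0.5 + f x c x (0.5 - p) x 0.5. The collected data give 0.5.

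| Scenario | f | True rate | Log shift | Type 2, SE | Eos >=0.3, SE |
|---|---|---|---|---|---|
| c = 1, p = 0 (ceiling) | 1% | 0.5025 | 0.0050 | 0.03 | 0.02 |
| | 5% | 0.5125 | 0.0247 | 0.13 | 0.11 |
| c = 1, p = 98/365.25 = 0.268 | 1% | 0.5012 | 0.0023 | 0.01 | 0.01 |
| | 5% | 0.5058 | 0.0115 | 0.06 | 0.05 |
| c = 0.25, p = 0 | 1% | 0.5006 | 0.0012 | 0.01 | 0.01 |
| | 5% | 0.5031 | 0.0062 | 0.03 | 0.03 |

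The 98 days are the end of the residual treatment epoch in Protocol 11.4.3.

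**Observation lost at the ceiling** (f x N x 0.5):

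- Type 2: 1.7 to 8.6 patient-years of 345 x 0.9 = 310.5, or 0.6% to 2.8%.
- Eosinophils >=0.3 Giga/L: 1.3 to 6.4 of 255 x 0.9 = 229.5.

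**The case against.** The strongest reply is that one sentence stands against its own heading, its own bullets and many other sections, so sites will have understood it as stopping IMP. That carries weight on likely conduct, and nothing in the documents shows a site obeying the sentence. It does not make the sentence right. It says *must*, while 10.3.4 describes return visits as something patients are asked and encouraged to make.

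Several limits on the consequence also stand:

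- SAP 2.3.1 drops efficacy data after unblinding, so code-break patients and the unblinded Brazilian patients lose nothing that the analysis would have used. If f includes them, the ceiling is overstated.
- Where a patient leaves the study, exceptional telephone follow-up with Sponsor approval remains possible: "During that phone contact, at least information about AEs, concomitant medication and asthma exacerbation events must be collected".
- Follow-up of serious events, events of special interest and pregnancies is required elsewhere.
- The pattern-mixture, control-based and tipping-point analyses in SAP 2.4.4.1 and Appendix D partly cover the missing data.
- Withdrawal reasons are already tabulated, and with timing summarized by arm (SAP 2.2 and 2.4.4.1).

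A reader might infer that every bullet, including any Sponsor request or protocol deviation, is really an IMP stop. The documents do not support that. Only yellow fever has such text among Sponsor requests; deviations and malignancy have none. Protocol 14.8.1 gives the Sponsor the right to end a site's participation or the study.

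**Conclusion.** The lead sentence of 10.3.3 is wrong as written. Confidence is high for the textual conflict and does not extend to how often sites acted on it. Where obeyed, the sentence leaves uncollected some exacerbations that the primary estimand counts, among patients stopped for pregnancy, allergic reaction, malignancy, opportunistic infection, the ALT criteria, or a Sponsor or deviation decision without unblinding.

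The effect is probably small: at most about 0.13 SE of the log rate ratio. That ceiling rests on an assumed 1% to 5% affected, superseded planning rates, withdrawal of every affected patient and immediate loss of drug effect. A reader might infer that the primary result is biased or that the trial lost a material amount of endpoint data. The documents do not support either inference: they give no frequency for these criteria and no evidence of site conduct, and the sample size already allows for more lost time than the ceiling. No power, sample size or alpha figure changes.

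**What to change.** Divide the list under two lead sentences.

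1. *Patients must be permanently discontinued from IMP and will be followed per Section 10.3.4* for: pregnancy, IMP-related anaphylactic or systemic allergic reaction, malignancy, opportunistic infection, the ALT/bilirubin criteria, code break by the Investigator, yellow fever, and a request to stop treatment only.
2. *Patients are withdrawn from the study* for: withdrawal of consent for follow-up (10.3.5), the Investigator's judgment that staying in the study is itself detrimental, and a Sponsor request or protocol deviation that specifically requires ending study participation. Other Sponsor requests and deviations default to the first list.

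The criteria stay the same, and no visits are added because 10.3.4 already schedules them. For malignancy, and for the default on Sponsor requests and deviations, the split settles a point on which the protocol has no separate text, so the Sponsor should confirm it.

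SAP Section 4 states that all patients have completed follow-up visits. If so, rewording recovers no data. An optional by-arm cross-table of reason for stopping IMP by study status at Week 52, in both primary populations, would show whether such patients left the study and whether the arms differ. It costs one table, and can be built only as far as the e-CRF categories allow; the documents do not show them.
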